10.7.4. Adverse Event Grading for Kidney Safety Laboratory Abnormalities

AE grading for decline in kidney function (ie, eGFR or eCrCl) will be according to Kidney Disease: Improving Global Outcomes (KDIGO) criteria for both pediatric and adult participants.

KDIGO criteria	Grade 1	Grade 2	Grade 3	Grade 4	Grade 5
Decreased Kidney Function due to either Acute or Chronic Kidney Injury	eGFR ≥ 90 mL/min/1.73m ² OR eCrCl ≥ 90 mL/min	eGFR ≥ 60 to 89 mL/min/1.73m ² OR eCrCl ≥ 60 to 89 mL/min	eGFR 30 to 59 mL/min/1.73m ² OR eCrCl 30 to 59 mL/min	eGFR 15 to 29 mL/min/1.73m ² OR eCrCl 15 to 29 mL/min	eGFR <15 mL/min/1.73m ² OR eCrCl <15 mL/min OR dialysis indicated
Albuminuria	Albuminuria <30 mg/g OR <3 mg/mmol	Albuminuria 30 to 300 mg/g OR 3 to 30 mg/mmol	Albuminuria >300 mg/gm OR <3 mg/mmol		

10.8. Appendix 8: ECG Findings of Potential Clinical Concern

ECG Findings That May Qualify as AEs

Marked sinus bradycardia (rate <40 bpm) lasting minutes.New PR interval prolongation >280 ms.New prolongation of QTcF to >480 ms (absolute).New prolongation of QTcF by >60 ms from baseline.New-onset atrial flutter or fibrillation, with controlled ventricular response rate: ie, rate <120 bpm.New-onset type I second-degree (Wenckebach) AV block of >30-second duration.Frequent PVCs, triplets, or short intervals (<30 seconds) of consecutive ventricular complexes.
ECG Findings That May Qualify as SAEs

QTcF prolongation >500 ms.Absolute value of QTcF > 450 ms AND QTcF change from baseline >60 ms.New ST-T changes suggestive of myocardial ischemia.New-onset LBBB (QRS complex >120 ms).New-onset right bundle branch block (QRS complex >120 ms).Symptomatic bradycardia.Asystole
In awake, symptom-free participants in sinus rhythm, with documented asystolic pauses ≥ 3 seconds or any escape rate <40 bpm, or with an escape rhythm that is below the AV node;In awake, symptom-free participants with atrial fibrillation and bradycardia with 1 or more asystolic pauses of at least 5 seconds or longer.Atrial flutter or fibrillation, with rapid ventricular response rate: rapid = rate >120 bpm.

- Sustained supraventricular tachycardia (rate >120 bpm) (“sustained” = short duration with relevant symptoms or lasting >1 minute).
- Ventricular rhythms >30 seconds’ duration, including idioventricular rhythm (HR <40 bpm), accelerated idioventricular rhythm (HR >40 bpm to <100 bpm), and monomorphic/polymorphic ventricular tachycardia (HR >100 bpm [such as torsades de pointes]).
- Type II second-degree (Mobitz II) AV block.
- Complete (third-degree) heart block.

ECG Findings That Qualify as SAEs

- Change in pattern suggestive of new myocardial infarction.
- Sustained ventricular tachyarrhythmias (>30-seconds duration).
- Second- or third-degree AV block requiring pacemaker placement.
- Asystolic pauses requiring pacemaker placement.
- Atrial flutter or fibrillation with rapid ventricular response requiring cardioversion.
- Ventricular fibrillation/flutter.
- At the discretion of the investigator, any arrhythmia classified as an adverse experience.

[figure not shown]
The major events of potential clinical concern listed above are recommended as “alerts” or notifications from the core ECG laboratory to the investigator and Pfizer study team, and not to be considered as all-inclusive of what is to be reported as AEs/ SAEs.

10.9. Appendix 9: Prohibited Concomitant Medications That May Result in DDI

PF-07853578 is primarily metabolized by CCI [REDACTED]. Therefore, as outlined in [Section 5.2](#) and [Section 6.9](#), use of prescription or nonprescription drugs and dietary and herbal supplements that are moderate or strong CCI [REDACTED] inducers or inhibitors are prohibited within 14 days plus 5 half-lives prior to the first dose of study intervention.

A non-exhaustive list of excluded moderate or strong CCI [REDACTED] inducers or inhibitors is below. Because this is not an all-inclusive list, site staff should consult with the sponsor or designee with any questions regarding potential DDI. The Pfizer study team is to be notified of any prohibited medications taken during the study.

CCI [REDACTED]

CCI

This list of drugs prohibited for potential DDI concerns may be revised during the course of the study with written notification from sponsor, to include or exclude specific drugs or drug categories for various reasons (eg, emerging DDI results for the IMP, availability of new information in literature on the DDI potential of other drugs), if the overall benefit:risk assessment is not impacted or if the changes do not significantly impact the safety of participants or the scientific value of the trial.

10.10. Appendix 10: Abbreviations

The following is a list of abbreviations that may be used in the protocol.

Abbreviation	Term
CCI	
Abs	absolute
ADL	activity/activities of daily living
AE	adverse event
AKI	acute kidney injury
ALT	alanine aminotransferase
ANOVA	Analysis of Variance
ASO	antisense oligonucleotides
AST	aspartate aminotransferase
AUC	area under the curve
AUC ₂₄	area under the plasma concentration-time curve from time 0 to 24 hours
AUC _{inf}	area under the plasma concentration-time curve from time 0 extrapolated to infinite time
AUC _{inf} (dn)	Dose-normalized AUC _{inf}
AUC _{last}	area under the plasma concentration-time curve from time 0 to the time of the last quantifiable concentration
AUC _{last} (dn)	Dose-normalized AUC _{last}
AV	atrioventricular
AxMP	auxiliary medicinal product
BAC-TG	bacterial artificial chromosome transgene
BBS	Biospecimen Banking System
CCI	
BID	twice daily
BMI	body mass index
BP	blood pressure
bpm	beats per minute
C _{av}	average plasma concentration
CDP	Clinical Development Plan
C _{eff}	efficacious concentration
CFR	Code of Federal Regulations
CIOMS	Council for International Organizations of Medical Sciences
CK	creatine kinase
CKD-EPI	chronic kidney disease epidemiology
C _{last}	last quantifiable concentration
CL/F	apparent oral clearance
CCI	
CL _p	plasma clearance
C _{max}	maximum plasma concentration
C _{max} (dn)	Dose-normalized C _{max}

Abbreviation	Term
CNS	central nervous system
CO ₂	carbon dioxide (bicarbonate)
COVID-19	coronavirus disease 2019
Cr	creatinine
CRF	case report form
CRO	contract research organization
CRU	clinical research unit
CSR	Clinical Study Report
CT	clinical trial
CTIS	Clinical Trial Information System
CYP	cytochrome P450
CYP3A	cytochrome P450 3A
CCI	
CCI	
DCT	data collection tool
DDI	drug drug interaction
DICI	drug-induced creatinine increase
DIKI	drug-induced kidney injury
DILI	drug-induced liver injury
dn	dose-normalized
DNA	deoxyribonucleic acid
EC	ethics committee
ECC	emergency contact card
ECG	electrocardiogram or electrocardiography
eCrCl	estimated creatinine clearance
eCRF	electronic case report form
EDB	exposure during breastfeeding
E-DMC	External Data Monitoring Committee
EDP	exposure during pregnancy
EDR	extemporaneous dispensing record
eGFR	estimated glomerular filtration rate
EMA	European Medicines Agency
eSAE	electronic serious adverse event
ET	early termination
EU	European Union
EudraCT	European Union Drug Regulating Authorities Clinical Trials (European Clinical Trials Database)
FDA	Food and Drug Administration
FIH	first-in-human
FSH	follicle-stimulating hormone
GCP	Good Clinical Practice
GGT	gamma-glutamyl transferase
GLP	Good Laboratory Practice

Abbreviation	Term
Hb	hemoglobin
HBcAb	hepatitis B core antibody
HBsAb	hepatitis B surface antibody
HBsAg	hepatitis B surface antigen
HCC	hepatocellular carcinoma
HCVAb	hepatitis C antibody
HDL	high-density lipoprotein
HIV	human immunodeficiency virus
HR	heart rate
HRT	hormone replacement therapy
IB	Investigator's Brochure
ICD	informed consent document
ICH	International Council for Harmonisation of Technical Requirements for Pharmaceuticals for Human Use
ID	identification
IDS	intermediate dosage strength
I_{max}	maximum inhibitory effect
IMP	investigational medicinal product
IND	Investigational New Drug
INR	international normalized ratio
IPAL	Investigational Product Accountability Log
IPM	investigational product manual
IQMP	integrated quality management plan
IRB	Institutional Review Board
IV	intravenous(ly)
KDIGO	Kidney Disease Improving Global Outcomes
K_{el}	elimination rate constant
LBBB	left bundle branch block
LDL	low-density lipoprotein
LFT	liver function test
MCH	mean corpuscular hemoglobin
MCHC	mean corpuscular hemoglobin concentration
MCV	mean corpuscular volume
MQI	medically qualified individual
NA	not applicable
NAFLD	nonalcoholic fatty liver disease
NASH	nonalcoholic steatohepatitis
NIMP	noninvestigational medicinal product
NOAEL	no-observed-adverse-effect level
NOEL	no-observed-effect level
CCI	
PCRU	Pfizer Clinical Research Unit
PD	pharmacodynamic(s)

Abbreviation	Term
PE	physical examination
CCI	
PGx	pharmacogenomic
PI	principal investigator
PK	pharmacokinetic(s)
PNPLA3	Patatin-like phospholipase domain-containing protein 3
PNPLA3-148M	isoleucine to methionine substitution at amino acid position 148 of the PNPLA3 protein
PNPLA3-WT	wildtype PNPLA3
CCI	
PROTAC	proteolysis targeting chimera
PSSA	Pfizer's Serious Adverse Event Submission Assistant
PT	prothrombin time
PVC	premature ventricular contraction/complex
QD	once daily
QTc	corrected QT interval
QTcF	QTc corrected using Fridericia's formula
qual	qualitative
RBC	red blood cell
RNA	ribonucleic acid
SAE	serious adverse event
SAP	Statistical Analysis Plan
Screat	serum creatinine
Scys	serum cystatin C
shRNA	small hairpin RNA
SoA	Schedule of Activities
SOP	standard operating procedure
SRSD	Single Reference Safety Document
SUSAR	suspected unexpected serious adverse reaction
t _½	terminal elimination half-life
TBD	to be determined
T bili	total bilirubin
CCI	
THC	tetrahydrocannabinol
T _{max}	time for C _{max}
UA	urine albumin
UACR	urine albumin/creatinine ratio
UGT	UDP-glucuronosyltransferase
ULN	upper limit of normal
US	United States
UTI	urinary tract infection
V _{ss}	volume of distribution at steady state

Abbreviation	Term
V_z/F	apparent oral volume of distribution
WBC	white blood cell
WOCBP	woman/women of childbearing potential
WT	wild-type

1. VERSION HISTORY

Table 1. Summary of Changes

Version/ Date	Associated Protocol Amendment	Rationale	Specific Changes
1	Final Protocol	N/A	N/A
23-Jun-2023	Amendment 1,		
	06 June 2023		

2. INTRODUCTION

This statistical analysis plan (SAP) provides the detailed methodology for summary and statistical analyses of the data collected in Study C5161001. This document may modify the plans outlined in the protocol; however, any major modifications of the primary endpoint definition or its analysis will also be reflected in a protocol amendment.

Text in *italics* is taken directly from the protocol.

2.1. Modifications to the Analysis Plan Described in the Protocol

No modifications.

2.2. Study Objectives, Endpoints, and Estimands

Type	Objective	Endpoint
	Primary:	Primary:
Safety Section 6.1	To evaluate the safety and tolerability of single ascending doses of PF-07853578 administered orally to healthy adult participants.	Assessment of AEs, clinical safety laboratory tests, vital signs, continuous cardiac monitoring, 12-lead ECGs, PEs, and neurological examinations.
	Secondary:	Secondary:
PK Section 6.2	To evaluate the PK of PF-07853578 following single doses of PF-07853578 administered orally to healthy adult participants.	PK parameters derived from plasma PF-07853578 concentrations: C_{max} , T_{max} , AUC_{last} , and if data permit, AUC_{inf} and $t_{1/2}$.
	Tertiary/Exploratory:	Tertiary/Exploratory:
PK Section 6.3.1	To evaluate additional PK parameters of PF-07853578 following single doses of PF-07853578 administered orally to healthy adult participants.	Additional PK parameters derived from plasma PF-07853578 concentrations: $C_{max}(dn)$, $AUC_{last}(dn)$, and if data permit, $AUC_{inf}(dn)$, CL/F , and V_z/F .
PK Section 6.3.2	To evaluate the effect of food on the PK of PF-07853578 following single doses of PF-07853578 administered orally to healthy adult participants (if conducted).	PK parameters derived from plasma PF-07853578 concentrations after a high-fat/high-calorie meal: C _{max} , T _{max} , AUC _{last} , and if data permit, AUC _{inf} and t _½ .
PK Section 6.3.3	To evaluate the PK of PF-07853578 following single oral doses of an IDS oral solution of PF-07853578 administered orally to healthy adult participants (if conducted).	PK parameters derived from plasma PF-07853578 concentrations after IDS oral solution dosing: C _{max} , T _{max} , AUC _{last} , and if data permit, AUC _{inf} and t _½ .

[figure not shown]
There are no estimands for this study.

2.3. Study Design

This study is a randomized, investigator- and participant-blind, sponsor-open, placebo-controlled, FIH, single ascending dose, 4-period, crossover, interleaving design study of PF-07853578 orally administered to healthy adult participants. Approximately 24 healthy adult participants (up to 3 cohorts of approximately 8 participants each) will be enrolled in this study. The optional third cohort will only be used if the objectives of the study are not fulfilled in Cohort 1 and Cohort 2. Each participant is planned to undergo 4 treatment periods receiving up to 4 doses of PF-07853578 and up to 2 doses of placebo. In each period, participants will be randomized to either PF-07853578 or placebo in a ratio of 6:2. A diagram of the study design is shown in Figure 1.

Precautionary sentinel dosing will be used in any period evaluating escalating doses of PF-07853578. Two participants (1 receiving PF-07853578 and 1 receiving placebo) within a period will be dosed initially before the remaining participants of that period are dosed. Safety and tolerability data through at least 24 hours post-dose for the sentinel participants will be reviewed prior to dosing the remaining participants of that period. Sentinel dosing may be omitted when repeating a dose level or administering a lower dose level than previously evaluated.

Figure 1. Study Design: Interleaving, Placebo-Controlled, 4-Period, Crossover Design

- Each period will consist of admission on Day -1, dosing on Day 1, and discharge at approximately 72 hours post-dose. Within a participant, there will be a washout interval of ≥10 days between doses.
- In each period, 6 participants will be randomized to receive PF-07853578, and 2 participants will be randomized to receive matching placebo.
- Precautionary sentinel dosing will be employed. Two participants (1 receiving PF-07853578 and 1 receiving placebo) within a period will be dosed initially before the
 remaining participants of that period are dosed. Safety and tolerability data through at least 24 hours post-dose for the sentinel participants will be reviewed prior to dosing
 the remaining participants of that period. Sentinel dosing may be omitted when repeating a dose level or administering a lower dose level than previously evaluated.
- The starting dose level in Period 1 of Cohort 1 is 1 mg. All other planned dose levels in other periods and cohorts may be adjusted pending emerging safety, tolerability, and PK data from previous periods and cohorts.
- Optional exploratory assessments: 1) effect of food on PF-07853578 PK and/or 2) evaluation of PK of an intermediate dosage strength oral solution of PF-07853578.
- Dose escalation to occur following review of PK data through at least 24 hours post-dose and safety and tolerability data through at least 48 hours post-dose of the current period. Cumulative safety and tolerability from all previous periods will also be reviewed.
- On-site follow-up visit to occur on 7-10 days after administration of the final dose of study intervention. Follow-up contact may occur via telephone contact and must occur 28-35 days after administration of the final dose of study intervention.

Screening activities will be completed over the 28 days prior to randomization in Period 1. In each period, participants will be admitted to the CRU on Day -1 and will remain in the CRU through at least the 72-hour assessments on Day 4. Participants may remain in the CRU after completion of Day 4 activities at the discretion of the investigator or if safety, tolerability, or PK data dictate the need to prolong confinement in the CRU. Participants will

receive a single oral dose of PF-07853578 or placebo on Day 1 of each period. Dose levels will be escalated to bracket the expected clinical dose range, but the projected exposures will not exceed the predefined human exposure limits. Within an individual participant, there will be a washout interval of at least 10 days between doses. The total duration of participation from the screening visit to the telephone follow-up contact will be approximately 17 weeks for each participant. Participants will return for an on-site follow-up visit 7-10 days after the final dose of study intervention. The follow-up contact may occur via telephone contact and must occur 28-35 days after administration of the final dose of study intervention.

Dosing will occur in the fasted state for all periods, except if an optional exploratory assessment of the effect of food on PF-07853578 PK is conducted. If the food effect is evaluated, it is anticipated that study intervention will be administered in the fed state in the last period of Cohort 2 or Cohort 3 at a dose level that was previously administered fasted within the same cohort. However, study intervention may be administered in the fed state during any of the study periods/cohorts if thought necessary to achieve study objectives. The actual dose level will be selected based on emerging safety, tolerability, and PK data but will be expected to achieve approximate projected therapeutic exposures.

If evaluated, the IDS oral solution of PF-07853578 is anticipated to be assessed in the last period of Cohort 2 or Cohort 3 at a dose level that was previously administered as a suspension within the same cohort. However, the IDS oral solution may be administered during any of the study periods/cohorts if thought necessary to achieve study objectives.

3. ENDPOINTS AND BASELINE VARIABLES: DEFINITIONS AND CONVENTIONS

3.1. Primary Endpoint(s)

Primary endpoints include assessment of adverse events (AEs) and treatment-emergent adverse events (TEAEs), clinical safety laboratory abnormalities, vital signs, ECG parameters, cardiac monitoring, and physical and neurological examinations during the entire study, by period.

Any events occurring following start of study intervention (ie, treatment with PF-07853578 or placebo) will be counted as treatment emergent.

Events that occur in a non-treatment period (eg, washout or follow-up) will be counted as treatment emergent and attributed to the most recent treatment taken.

A 3-tier approach for summarizing adverse events (AEs) will not be used due to the low number of participants planned to be recruited.

The following data are considered in standard safety summaries (see protocol for collection days and list of parameters):

- adverse events,
- laboratory data (except data from screening visit),
- vital signs data,

- ECG results,
- cardiac monitoring,
- physical examinations,
- neurological examinations.

3.1.1. Adverse Events

An AE is considered a TEAE if the event started during the effective duration of treatment. All events that start on or after the first dose of study intervention, but before the end of the study will be flagged as TEAEs. The algorithm will not consider any events that started prior to the first dose date.

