10.3.1. Definition of AE

AE Definition

- An AE is any untoward medical occurrence in a patient or clinical study participant, temporally associated with the use of study intervention, whether or not considered related to the study intervention.
- Note: An AE can therefore be any unfavorable and unintended sign (including an abnormal laboratory finding), symptom, or disease (new or exacerbated) temporally associated with the use of study intervention.

Events Meeting the AE Definition

- Any abnormal laboratory test results (hematology, clinical chemistry, or urinalysis) or other safety assessments (eg, ECG, radiological scans, vital sign measurements), including those that worsen from baseline, considered clinically significant in the medical and scientific judgment of the investigator. Any abnormal test results that meet any of the conditions below must be recorded as an AE:
 - Is associated with accompanying symptoms;
 - Requires additional diagnostic testing or medical/surgical intervention;
 - Leads to a change in study dosing (outside of any protocol-specified dose adjustments) or discontinuation from the study, significant additional concomitant drug treatment, or other therapy.
- Exacerbation of a chronic or intermittent preexisting condition, including an increase in either frequency and/or intensity of the condition.
- New condition detected or diagnosed after study intervention administration, even though it may have been present before the start of the study.
- Signs, symptoms, or the clinical sequelae of a suspected drug-drug interaction.
- Signs, symptoms, or the clinical sequelae of a suspected overdose of either study intervention or a concomitant medication. Overdose per se will not be reported as an AE or SAE unless it is an intentional overdose taken with possible suicidal/self-harming intent. Such overdoses should be reported regardless of sequelae.

Events NOT Meeting the AE Definition

- Any clinically significant abnormal laboratory findings or other abnormal safety assessments that are associated with the underlying disease, unless judged by the investigator to be more severe than expected for the participant's condition.
- The disease/disorder being studied or expected progression, signs, or symptoms of the disease/disorder being studied, unless more severe than expected for the participant's condition.
- Medical or surgical procedure (eg, endoscopy, appendectomy): the condition that leads to the procedure is the AE.

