- It is not acceptable for the investigator to send photocopies of the participant's medical records to Pfizer Safety in lieu of completion of the CT SAE Report Form/AE or SAE CRF page.

- There may be instances when copies of medical records for certain cases are requested by Pfizer Safety. In this case, all participant identifiers, with the exception of the participant number, will be redacted on the copies of the medical records before submission to Pfizer Safety. Refer to [Section 10.1.9](#) for actions that must be taken when medical records are sent to the sponsor or sponsor designee.
- The investigator will attempt to establish a diagnosis of the event based on signs, symptoms, and/or other clinical information. Whenever possible, the diagnosis (not the individual signs/symptoms) will be documented as the AE or SAE.

Assessment of Intensity

The investigator will make an assessment of intensity for each AE and SAE reported during the study and assign it to 1 of the following categories:

- Mild: A type of AE that is usually transient and may require only minimal treatment or therapeutic intervention. The event does not generally interfere with usual ADL.
- Moderate: A type of AE that is usually alleviated with additional specific therapeutic intervention. The event interferes with usual ADL, causing discomfort, but poses no significant or permanent risk of harm to the research participant.
- Severe: A type of AE that interrupts usual ADL, or significantly affects clinical status, or may require intensive therapeutic intervention.

An event is defined as “serious” when it meets at least 1 of the predefined outcomes as described in the definition of an SAE, NOT when it is rated as severe.

Assessment of Causality

- The investigator is obligated to assess the relationship between study intervention and each occurrence of each AE or SAE. The investigator will use clinical judgment to determine the relationship.
- A “reasonable possibility” of a relationship conveys that there are facts, evidence, and/or arguments to suggest a causal relationship, rather than a relationship cannot be ruled out.
- Alternative causes, such as underlying disease(s), concomitant therapy, and other risk factors, as well as the temporal relationship of the event to study intervention administration, will be considered and investigated.

- The investigator will also consult the IB and/or product information, for marketed products, in their assessment.

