- For each AE or SAE, the investigator **must** document in the medical notes that they have reviewed the AE or SAE and have provided an assessment of causality.
- There may be situations in which an SAE has occurred and the investigator has minimal information to include in the initial report to the sponsor. However, it is **very important that the investigator always make an assessment of causality for every event before the initial transmission of the SAE data to the sponsor.**
- The investigator may change their opinion of causality in light of follow-up information and send an SAE follow-up report with the updated causality assessment.
- The causality assessment is one of the criteria used when determining regulatory reporting requirements.
- If the investigator does not know whether or not the study intervention caused the event, then the event will be handled as “related to study intervention” for reporting purposes, as defined by the sponsor. In addition, if the investigator determines that an SAE is associated with study procedures, the investigator must record this causal relationship in the source documents and CRF, and report such an assessment in the dedicated section of the CT SAE Report Form and in accordance with the SAE reporting requirements.

Follow-Up of AEs and SAEs

- The investigator is obligated to perform or arrange for the conduct of supplemental measurements and/or evaluations, as medically indicated or as requested by the sponsor, to elucidate the nature and/or causality of the AE or SAE as fully as possible. This may include additional laboratory tests or investigations, histopathological examinations, or consultation with other healthcare providers.
- If a participant dies during participation in the study or during a recognized follow-up period, the investigator will provide Pfizer Safety with a copy of any postmortem findings, including histopathology.
- New or updated information will be recorded in the originally submitted documents.

- The investigator will submit any updated SAE data to the sponsor within 24 hours of receipt of the information.

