6.1. Primary Endpoint(s)

6.1.1. Adverse Events

AEs will be summarized by dose and treatment (if applicable) and overall and in accordance with sponsor reporting standards using the safety population defined in Section 4.

Incidence and severity of TEAE tables will additionally be produced ('All causality' and 'Treatment related,' separately) to summarize the total number of adverse events by preferred term, which will be reported by dose and treatment (if applicable) and overall, in accordance with sponsor reporting standards using the safety analysis set defined in Section 4.

The AEs will be presented sorted in descending frequency based on the overall number of AEs (by preferred term or system order class as appropriate) across treatments.

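### The TEAE rule looks only at when an event started, so an AE kept on one record that worsens after a later dose is missing from that dose's tables

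*SAP*

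**What the plan says.** SAP 3.1.1 defines treatment emergence by onset: "An AE is considered a TEAE if the event started during the effective duration of treatment". It flags events that start on or after the first dose and before the end of the study, and closes with "The algorithm will not consider any events that started prior to the first dose date". The term for the treatment window is not defined further.

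SAP 3.1 adds that events in a non-treatment period, such as washout or follow-up, "will be counted as treatment emergent and attributed to the most recent treatment taken". Nothing is said about an event that spans two doses and changes in severity.

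SAP 6.1.1 plans AE summaries by dose and treatment, and then: "Incidence and severity of TEAE tables will additionally be produced". It refers to sponsor reporting standards for detail. It does not say whether the severity tables use the first grade, the worst grade, or the grade in each period.

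On recording, Protocol 10.3.3 says "The investigator will make an assessment of intensity for each AE and SAE reported during the study" and, under follow-up, "New or updated information will be recorded in the originally submitted documents". Protocol 10.3.1 lists among events that meet the AE definition "Exacerbation of a chronic or intermittent preexisting condition, including an increase in either frequency and/or intensity". Protocol 8.4.1 starts AE collection at informed consent, so AEs before the first dose can exist.

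**The concern.** A start-date rule is adequate for events with new onset. It is less suited to a four-period crossover, where three of each participant's four doses go to someone who may still have an open AE, and the first dose may follow an AE recorded since consent. The Schedule of Activities expects this, since it provides for brief physical examinations for new or open AEs in later periods.

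The SAP treats its other safety data differently. Baselines for laboratory tests, vital signs and ECG are reset in every period (SAP 3.1.2 to 3.1.4), so a deterioration after a later dose is measured against that period's own baseline. AEs, the first item in the primary endpoint, have no equivalent.

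At stake is how faithfully the TEAE tables show incidence and severity by dose. These are a main output for the primary objective in a study with no hypothesis test.

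**Working it through.** No stated figure has to be reproduced. The check applies the rule as written, then sizes it.

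**1. The rule applied to three records, each kept as one record with one start date**

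| Record | Result under SAP 3.1 and 3.1.1 |
|---|---|
| Mild headache starts in screening, becomes severe after the first dose | Started before the first dose date: not a TEAE at any dose |
| Mild headache starts after the Period 2 dose, still open, becomes severe after the Period 3 dose | TEAE, placed with the Period 2 treatment; no event at the Period 3 treatment |
| New headache starts after a dose | TEAE, placed with that dose: correct |

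In the second record the Period 2 entry is right in itself; the Period 3 entry is what is missing. If the worst grade is tabulated, Period 2 also carries a severity that arose after the Period 3 dose. If the initial grade is tabulated, the worsening appears nowhere in the severity table.

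**2. The same records if the worsening is entered as a new AE**

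The new record starts after the later dose, and the existing rule places it correctly. The result therefore depends on a recording convention that neither document fixes.

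**3. Size of one event**

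Protocol 4.1 gives cohorts of about 8 and a 6:2 ratio, so 8 × 6/8 = 6 active participants per dose level. One participant missing from a row of the table moves that row by 1/6 = 16.7 percentage points.

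**4. Direction**

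Count placebo as dose zero. A cohort of 8 over 4 periods has 8 × 3 = 24 dose-to-dose transitions.

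- *Every period escalates.* The earlier treatment is lower whenever the later one is active, whether the earlier one was placebo or a lower dose. That is 6 × 3 = 18 of 24 = 75%, for any allocation sequence. In the other 6 the later treatment is placebo.
- *The last period repeats an earlier dose level* (the optional fed or IDS period in Protocol 4.1). Transitions into Periods 2 and 3 give 6 × 2 = 12. Into Period 4 the earlier treatment is lower only for someone on placebo in Period 3 and active in Period 4, which is 0 to 2 participants. The total is 12 to 14 of 24, or 50% to 58%.

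These are shares of opportunities, not of events. The design figure is not reproduced in the available text; the 75% does not depend on the sequences, while the place within 50% to 58% does.

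**5. Number of events**

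The documents give no worsening rate. Active doses number 2 × 4 × 6 = 48 with two cohorts and 3 × 4 × 6 = 72 with the optional third. If 1% to 5% of active doses were given to someone whose open AE then worsened (an assumption), the count would run from 48 × 0.01 = 0.5 to 72 × 0.05 = 3.6, and only where the worsening stays on the original record.

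**The case against.** The strongest reply is that the misplacement is not automatic. The exacerbation item in Protocol 10.3.1 supports treating the worsening of a preexisting condition as an AE in its own right, with a start after the dose. The sentence in 10.3.3 about updating the original documents sits among SAE follow-up instructions and does not clearly tie a worsened AE to one record and one onset date. The CRF Completion Requirements named in Protocol 10.1.7 may settle the matter, but are not available. This stands, and it makes the problem conditional. It does not remove it: the exacerbation item does not plainly reach an AE that arose earlier in the study, and no text tells sites to open a new record.

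The number of cases is also likely to be low. Participants are healthy, each dose is single, and doses are at least 10 days apart. That stands too.

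A reader might infer more than the documents support:

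- *The event is charged to the earlier dose at its worst severity.* No worst-grade rule is stated.
- *Events that began before the first dose are lost.* They are absent only from the TEAE tables. They stay on the CRF and in any general AE summary under SAP 6.1.1.
- *Laboratory worsening is hidden as well.* Laboratory baselines reset each period and laboratory data are summarized separately by dose (SAP 3.1.2 and 6.1.2), so a change after the later dose would still show there.
- *Escalation and stopping are affected, because Protocol 6.6.1 counts severe AEs by dose level.* Those decisions rest on review by the study team and the investigator (Protocol 6.6 and 6.6.1), and no text ties them to the TEAE flag.

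**Conclusion.** The point holds in a conditional form. SAP 3.1.1 gives an explicit rule that places a post-dose worsening wrongly whenever the AE stays on one record, and neither document requires otherwise. An AE that began before the first dose then has no place in the TEAE tables, and one that began after an earlier dose stays with that treatment.

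The consequence is limited to the descriptive by-dose TEAE incidence and severity tables: 16.7 points per participant at an active dose level with 6 treated, for an unknown and probably small number of events.

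A reader might infer a consistent bias that flattens the dose-severity relationship. The documents support only a tendency. The earlier treatment is the lower one in 75% of transitions under full escalation, but in about half or a small majority if the last period repeats a dose level. Where the later treatment is placebo, it is placebo that is understated.

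**What to change.** In SAP 3.1.1:

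- Define an AE as treatment-emergent for a dose if it starts after that dose, or if it started earlier (including before the first dose) and increases in severity after that dose and before the next.
- Attribute the increased severity to that dose, and leave the earlier severity with the earlier treatment or with pre-treatment.
- State that the severity tables use the highest grade within each treatment period.
- Delete the sentence that excludes all events that started before the first dose date.

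The program needs a date for the worsening. The CRF completion guidance should therefore require either a new linked AE record or a dated severity change on the existing one, worded consistently with Protocol 10.3.3.

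The cost is a few sentences in the SAP and an instruction in the CRF guidance, with no added visits, samples or participants. Linked records would raise event counts slightly, but not participant counts. The change should be made before analysis, so that individual cases are not settled later by a sponsor team that is already unblinded.
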